Based on the IMB Model (information, motivation, behavioral skills) and the theory of planned behavior addressing normative behaviors (Ajzen & Fishbein, 1980) this exploratory study will examine the factors (e.g., father's circumcision and HIV status, paternal grandparents' and peer circumcision attitudes, mother's HIV status and circumcision attitudes) that underlie the decision to engage in VMMC and EIMC, and tailor the LFLS intervention component to respond to these factors. The study will offer S&S + LFLS to pregnant couples, targeting the perinatal period to address MC for both father and son(s), and pilot test the biobehavioral program, assessing feasibility of offering S&S+LFLS in Lusaka Province CHCs, the acceptability of the pilot program, and the potential of S&S+LFLS to optimize both VMMC and EIMC uptake.

Innovation

This application includes a number of innovative components. Promoting the bonding component of the father-son relationship, this application simultaneously addresses both the short and long-term HIV risk reduction goals associated with increasing availability and acceptability of male circumcision. We are unaware of any evidence-based effort in sub-Saharan Africa to stimulate prospective parents to simultaneously consider both EIMC and VMMC. The S&S + LFLS intervention could stimulate both EIMC and VMMC to occur during the pre- and immediate postnatal period, prior to resuming sexual activities, which corresponds with both mother and father undergoing healing following childbirth and VMMC, respectively. (N.B.: Our previous research found approximately 25% of the men undergoing VMMC were unable to abstain from sexual activities for the 6-week healing period; this group accounted for the majority of adverse events and dissatisfaction with VMMC). As most Zambian men are uncircumcised, a combined VMMC/EIMC program could encourage prospective fathers choosing to undergo VMMC to circumcise their male neonates, as well as other sons, procedures that would render their penises identical. Among men already circumcised, the program provides additional support for EIMC and VMMC for other sons. Finally, this program includes community health center EIMC sensitization, training and behavioral interventions, optimizing the impact of demand generation on uptake.

Impact

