Participants will meet with study staff and will be verbally screened for eligibility based on the following criteria, by study staff at each clinic.

CAB participants: CABs operate in each CHC clinic and are comprised of community zone leaders in the clinic catchment area; as zone leaders, they educate their community on the study objectives and sensitize their community on study goals, risks and benefits. Eligible CAB members will be men and women aged >18, representing a ward within each experimental CHC site catchment area. Twenty Community Advisory Board (CAB) member participants will be recruited from CABs at each clinic (20 CAB members x 4 clinics, n = 80), and each attendee will be compensated ~\$US10 per visit.

Focus Group participants. Stakeholder participants will be recruited from ANCs to attend gender specific focus group discussions (FGDs). A total of 8 pregnant couples from each of the 4 experimental CHC clinics (8 couples per clinic) will be recruited for this study [2 gender specific FGDs per clinic; (8 men and 8 women) x 4 clinics = 64 participants]. Both members of each couple must enroll to participate. Eligible participants will be pregnant couples (men and pregnant female partners) aged >18, attending the antenatal clinic of the experimental CHC. No personal, individually identifying information will be collected and no individual interviews or assessments will be conducted with FGD Members. Each attendee will be compensated ~\$US10 per visit.

IRB Study Number:

Version #, Date:

S&S+LFLS Participants. Pregnant couple participants (300 couples, n = 600 participants) will be recruited over 18 months via referral from ANC/VCT and enrolled as couples. A total of 75 pregnant couples will be recruited from each of the 4 clinics participating in LFLS (75 pregnant couples per clinic x 4 clinics = 300 couples = 600 individual men and women.) Both members of each couple must enroll to participate. Eligible women will be pregnant (up to 6 months pregnant), aged >18, any HIV status, and the partner of a male participant enrolling (neonates undergoing EIMC are receiving a clinical service approved by parents; only parents are study participants). Eligible men will be aged > 18, any HIV status [in accordance with Zambian and WHO/UNAIDS (2016) policy for MC eligibility], and the partner of the pregnant female participant enrolling. There is no upper age limit for participation, and each person will be compensated ~\$US10 per visit.

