Pregnant Couple Members attending LFLS. All S&S+LFLS study participants will be followed from enrollment to six months post-partum (maximum ~ time of participation based on enrollment at ~3-4 months pregnant = 12 months). Participants will complete baseline, pre-and post-partum and 6-months post-partum assessments and attend the Spear & Shield and 2 LFLS intervention sessions (see below).

Enrollment will be conducted from month 7 – 24, a total of 18 months.

11) **Study Endpoints***

Primary and secondary study endpoints.

Primary endpoints.

- EIMC uptake (infant)
- VMMC uptake (father and other sons)

Secondary endpoints.

- Father's and mother's circumcision attitudes

Primary or secondary safety endpoints.

This is a behavioral feasibility study, not requiring safety endpoints.

12) **Procedures Involved***

Design.

Like Father Like Son(s) proposes to develop intervention materials and test the effectiveness of the intervention to enhance the uptake of early infant male circumcision (EIMC) and voluntary medical male circumcision (VMMC) in the community health center (CHC) setting.

The study utilizes a longitudinal repeated measures design [2 (condition) x 4 (time points)]. The pilot study intervention will expand the Spear & Shield (S&S) intervention to include the “Like Father Like Son” component (S&S + LFLS).

IRB Study Number:

Version #, Date:

The pilot study will randomize 8 clinics to Experimental and Observation conditions; clinics will be matched on catchment area size and current EIMC and VMMC rates.

Experimental clinics (n = 4) will be trained to offer “S&S+LFLS”; Observation clinics (n = 4) will be “Observation Only” sites. Observation only sites will not recruit participants and will only be “observed” regarding the total number of VMMCs and EIMCs conducted at each individual clinic - Observation Only clinics will only provide clinic level aggregate data.

The study will train both Experimental and Observation Only clinic staff to conduct VMMC and EIMC procedures in order to provide equivalent services at all clinics, controlling for the availability of circumcision at all sites. Participants will only be recruited from experimental sites. The study will also assess the feasibility and acceptability of offering S&S+LFLS at the CHC level, and if successful, plan for a clinical trial of the S&S+LFLS intervention.

CAB Meetings & Focus Groups.

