Following baseline assessments, couples will complete a brief Stages of Change questionnaire prior to each prenatal and one-week post-partum LFLS sessions. Couples will be assessed at 6 months post-partum to evaluate EIMC and VMMC uptake by father, sons and infant to examine the interactive influence of EIMC and VMMC uptake, as well as the role of both parents, family members, peers and HIV serostatus in the decision-making process (Montaño et al., 2018; Mavhu et al. 2017; Cook et al., 2015; [name], Cook et al., 2014) (see Assessments).

13) Data and Specimen Banking* n/a

14) Data Management*

Analytic Plan and Power Analysis

Aim 1. Develop, pilot and conduct formative, process and outcome evaluations to assess the CHC level feasibility and acceptability of S&S+LFLS.

Aim 2. Assess the intrapersonal, interpersonal, structural, and sociocultural factors relevant to the LFLS intervention, and develop program components to respond to these factors.

Hypothesis 2. Father's circumcision status, paternal grandparents' circumcision attitudes, peer circumcision attitudes, father's HIV status, and mother's HIV status will be indirectly related to the decision to choose EIMC through the father's circumcision attitudes. A mother's circumcision attitudes will be influenced by her HIV status, and her protective attitudes toward the newborn which will also influence the father's circumcision attitudes.

Aim 3. Assess whether the combined S&S + LFLS pilot program will increase uptake of EIMC at clinic level.

Hypothesis 3. The S&S + LFLS experimental condition clinics will have significantly higher numbers of EIMC in comparison with observation condition clinics.

Hypothesis testing. The analyses for this feasibility pilot study will begin with examination of frequencies, means, skewness, and kurtosis across study variables (EIMC, VMMC, HIV status, attitudes) to assess normality. We will conduct 1) analysis of qualitative data, 2) a path model to explore undergirding sociocontextual factors of a father's decision to elect EIMC or VMMC for his male children, 3) a test of comparison between conditions.

IRB Study Number:

Version #, Date:

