H2. Assess factors relevant to the LFLS model. To investigate the indirect effects of the five main predictors (paternal grandparents' circumcision attitudes, peer attitudes surrounding circumcision, father's HIV status, father's circumcision status, and mother's HIV status) on infant circumcision, a path analysis (Kline, 2011) will be conducted. To estimate the indirect effects, it will be specified that the paths between the five main predictors on infant circumcision will act through father's circumcision attitudes. Mother's circumcision attitudes will be regressed on mother's HIV status, and a regression path between father's and mother's attitudes toward circumcision will be specified. When estimating the indirect effects, results will be adjusted for the effect of number of siblings circumcised.

All potential indirect effects will be estimated by a bootstrapping approach (MacKinnon et al., 2007). R-square of indirect effects will be used as measures of effect size (Fairchild et al., 2009). A sandwich estimator will be used to account for the nested data structure (e.g., individuals are nested by clinics). This estimator uses the Huber/White correction and adjusts for potential underestimated standard errors and bias in chi-square computation (Liang & Zeger 1986).

Missing data will be handled using Full Information Maximum Likelihood estimation procedures (Enders & Bandalos 2001). For model fit evaluations, we will use well-established fit indices and cutoff values: A well-fitting model ideally will have a non-significant model χ^2 , a Comparative Fit Index / Tucker-Lewis Index greater than .95, a root mean square error of approximation less than .08, and a standardized root mean square residual less than .08 (Hooper et al., 2008). All analyses will be conducted in Mplus (V8; Muthén & Muthén, 2017).

H3. Effect of S&S + LFLS pilot. To compare the proportion of EIMCs in the experimental group to the proportion found in the observation group, a one-sample z-test will be conducted. The population proportion will be taken to be the midpoint of the findings from Waters et al. (2013) on neonatal circumcision and historical numbers of circumcisions from Zambian clinics and hospitals. Based upon this rationale, the percentage of EIMCs in the observation group is anticipated to be approximately 5.0%.

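### H2's component paths are tested with a clinic-level sandwich built from only four clinics (about 14–24% false positives at an assumed 5% level), and the bootstrap unit for the indirect effects is not stated

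*Combined protocol and SAP*

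**What the plan says.** Section 14 (H2) sets out a path analysis in which five predictors act on infant EIMC through father's attitudes. In addition, "Mother's circumcision attitudes will be regressed on mother's HIV status", and a path joins mother's and father's attitudes. On standard errors it says: "A sandwich estimator will be used to account for the nested data structure (e.g., individuals are nested by clinics". It adds that this Huber/White estimator deals with standard errors that may be too small and with bias in the chi-square. It names no small-sample factor, reference distribution or alpha for H2; the two-tailed .05 under Power belongs to the comparison of EIMC proportions (H3).

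On the indirect effects: "All potential indirect effects will be estimated by a bootstrapping approach". The resampling unit is not given.

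On the number of clinics, section 7 says "A total of 75 pregnant couples will be recruited from each of the 4 clinics participating in LFLS" and section 12 (Design) says "Participants will only be recruited from experimental sites". Observation clinics supply aggregate counts only, so they add no clusters to H2.

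On the status of H2, section 14 describes "a path model to explore undergirding sociocontextual factors". Aim 2 ends "and develop program components to respond to these factors", and section 6 says the study will examine such factors "and tailor the LFLS intervention component to respond to these factors".

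**The concern.** A cluster-robust variance is trustworthy when there are many clusters. With four, it is estimated from four clinic totals that carry three independent pieces of information. It is then both noisy and biased downwards, and adding couples per clinic does not help. The estimator the plan chose to repair standard errors that are too small therefore produces them, even if outcomes do not vary by clinic at all. The chi-square adjustment has the same weakness: the clinic-level score matrix has rank at most 3, while the father's-attitude equation has seven parameters (an intercept and six regressors).

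The bootstrap raises a separate question. Resampling clinics would be the natural match to a clinic-level sandwich, but it performs badly with four clinics. Resampling couples does not. The plan leaves this open.

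At stake is which family and HIV-status factors are reported as related to circumcision attitudes, and so possibly what a later version of the program responds to.

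**Working it through.** **1. The plan's own figure.** None is given for H2. The only stated power is for H3, and it supplies two inputs used below: uptake of 5.0% + 6.0 points = 11%, and about 151 couples with male infants. It reproduces as a one-sample z-test with n = 140: Φ[(0.06 − 1.96√(0.05×0.95/140)) / √(0.11×0.89/140)] = Φ[(0.0600 − 0.0361)/0.0264] = Φ(0.904) = 81.7%, against a stated figure of over 80%.

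**2. Inputs.**
- From the documents: G = 4 clinics; 75 couples per clinic, or 151/4 ≈ 38 with a male infant; HIV prevalence 20.8% (section 24); circumcision rate 22% (section 6); uptake 11% or 5%.
- Assumed: normal reference, two-sided 5%; intraclass correlation 0 to 0.10 for outcomes and predictors; clinic SD 0 to 0.6 on the logit scale for EIMC.

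**3. Analytic rate.** With the factor G/(G−1), the statistic behaves roughly like t on G−1 = 3 df: P(|t₃| > 1.96) = 14.5%. Without the factor the standard error shrinks by √(3/4): P(|t₃| > 1.96×√0.75 = 1.70) = 18.8%.

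**4. Simulated false-positive rates (%), nominal 5%.** The first two result columns use a normal reference.

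| Path | Sandwich, no factor | With G/(G−1) | G/(G−1) and t(3) | Clinic indicators, couple-level SE |
|---|---|---|---|---|
| Mother's attitudes on HIV, 4×38 | 18.9–21.6 | 15.0–16.9 | 5.4–6.3 | 4.7–5.4 |
| Same, 4×75 | 19.2–21.2 | 14.7–16.5 | 4.8–5.8 | 4.6–5.6 |
| Father's attitudes, 6 regressors, 4×38 | 18.8–22.8 | 14.4–17.8 | 4.7–6.8 | 4.4–6.0 |
| Same, 4×75 | 18.3–24.0 | 13.7–19.2 | 4.6–6.9 | 4.3–6.0 |
| EIMC on father's attitudes (logistic, 11%), 4×38 | 19.8–22.9 | 15.4–17.9 | 5.1–6.3 | 4.9–5.2 |

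These used 6,000, 3,000 and 4,000 data sets per setting for the mother's, father's and EIMC paths. The indicator run for EIMC used a small ridge penalty (0.01) on the indicators. Without indicators, couple-level standard errors in the EIMC equation gave 4.5–6.2%. At 5% uptake a two-predictor EIMC path under the sandwich gave 18.9% with the factor and 23.1–23.8% without; a further run reached about 26%.

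In a seven-predictor attitude equation, couple-level errors without indicators drifted up to 8.2% at intraclass correlation 0.10 and 75 couples per clinic. That is why indicators are worth having there.

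**5. Indirect effects.** Percentile bootstrap, 399 draws, 700–800 data sets, binary EIMC at 11%, one of the two paths set to zero:
- resampling couples: 3.9–9.1%
- resampling couples within clinic, with indicators: 3.9–9.0%
- resampling clinics: 14.1–21.7%

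With both paths zero (300 data sets), the rates were 0.3–1.0% for couples and 3.0–4.7% for clinics. Four clinics allow only C(7,4) = 35 distinct resamples, and 4/4⁴ = 1.6% of draws are one clinic repeated four times.

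**6. Can the EIMC equation carry clinic indicators?** Chance that at least one clinic of 38 has no EIMC, with no clinic effect:
- 11% uptake: 1 − (1 − 0.89³⁸)⁴ = 1 − (1 − 0.0119)⁴ = 4.7%
- 5% uptake: 1 − (1 − 0.95³⁸)⁴ = 1 − (1 − 0.1424)⁴ = 45.9%

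At clinic SD 0.6 the first rises to about 20%. At 5% uptake simulations gave about 44–54%, and one at SD 0.6 gave about 63%. Even when every clinic has an event, within-clinic bootstrap draws contain a zero-event clinic in 18–27% of draws at 11% uptake and about 53% at 5%. Indicators then separate.

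**Limits.** Data were complete and equations were fitted one at a time, not in Mplus and not with the joint full-information likelihood model the plan specifies.

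**The case against.** **The sandwich is not the main H2 test.** H2 is chiefly about indirect effects, and these are bootstrapped. A reader might infer that H2 as a whole runs at 14–24%. The documents do not support that: no section proposes resampling clinics, and resampling couples gives 4–9%. This objection stands. For the indirect effects the fault is an unstated detail. It does not cover H2's second sentence, which makes two component paths hypotheses in their own right.

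**The consequence is limited.** A reader might infer that chance findings would shape the sessions delivered in this study. Section 12 says the sessions are built from focus groups, advisory boards, clinic staff and existing research, and section 10 puts data analysis in months 31–36, beside preparation of the follow-on application. No go/no-go rule depends on H2. This stands, and what remains is a possible influence on a later version of the program.

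**A count of false findings overstates the matter.** Eight component paths give 8×0.137 = 1.1 to 8×0.240 = 1.9 expected false positives, against 8×0.05 = 0.4. That is an upper bound which holds only if all eight paths are null, and section 6 cites evidence that father's circumcision status is the leading determinant of EIMC.

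**The wording and software leave room.** Clinics are introduced only as an example of nesting, but no other unit is named. If the software used a t(3) reference the rate would be about 5–7%, but the plan does not call for one. Under a normal reference the rate is inflated with or without G/(G−1).

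**Conclusion.** The point holds for the component paths, and the rule is wrong as written. With a normal reference and a two-sided 5% level (both assumed), false-positive rates are about 14–24% at 11% uptake and reach about 26% for the EIMC path at 5% uptake. The inflation comes from having four clusters, so it is present at zero intraclass correlation and at both 38 and 75 couples per clinic. The spread reflects the assumed clustering and whether G/(G−1) is applied.

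The two component paths that H2 states outright are the ones most affected. The indirect-effect tests are near nominal to mildly inflated under a couple bootstrap and seriously inflated only under a clinic bootstrap; the plan needs to say which it uses. H2 is exploratory and H3 does not use this estimator, so the study's main comparison is untouched. The correction is cheap and should be made before analysis.

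**What to change.** Amend section 14 (H2) as follows.

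- **Two attitude equations:** replace the clinic-level sandwich with three clinic indicators and couple-level standard errors, either model-based or heteroscedasticity-robust. Base the model fit test on the same couple-level estimator.
- **EIMC equation:** use couple-level standard errors without clinic indicators, since a clinic with no EIMCs is a realistic prospect, in the data and within bootstrap draws.
- **Indirect effects:** bootstrap couples within clinic, not clinics.
- **State** the alpha level and reference distribution for H2.

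The cost is three extra parameters in each attitude equation and a small loss of power. Simulated power for the indirect effect was 85–94% with indicators and within-clinic resampling, against 88–93% resampling couples without indicators. Omitting indicators from the EIMC equation costs nothing: at an odds ratio of 2.0 per SD of father's attitudes and about 17 events (152×0.11), power was 69–70% without indicators and 68–70% with them. The exact combination proposed, with indicators in the attitude equations only, was not itself simulated; the arrangements on either side of it both gave 4–9% for the indirect effects.

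Keeping the sandwich with G/(G−1) and a t(3) cutoff of 3.18 would also control the error rate, but at a high price. For a 0.5 SD attitude difference by mother's HIV status, power falls to 42–44% from 70% with indicators in 152 couples, and to 66–67% from 93–95% in 300. No change to design, sample size or data collection is needed.

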Hypothesis 2. Father’s circumcision status, paternal grandparent’s circumcision attitudes, peer circumcision attitudes, father’s HIV status, and mother’s HIV status will be indirectly related to the decision to elect EIMC through **the father’s circumcision** attitudes. A mother’s circumcision attitudes will be influenced by her HIV status, and her attitudes will also influence the father’s circumcision attitudes.

Aim 3. Assess whether the combined S&S + LFLS pilot program will increase uptake of EIMC at the clinic level.

Hypothesis 3. The S&S + LFLS experimental condition clinics will have higher numbers of EIMC in comparison with observation condition clinics.

6) Background*

Voluntary medical male circumcision (VMMC). Randomized clinical trials involving over 11,000 adult men in Uganda, Kenya and South Africa have confirmed that voluntary medical male circumcision (VMMC) provides upwards of 60-73% protection for men from HIV infection (Auvert et al., 2005; Bailey et al., 2007; Gray et al., 2007; [name] et al., 2000). Yet, despite these encouraging findings, the majority of Zambian men remain reluctant to circumcise ([name] et al., 2015; [name] et al., 2015; Republic of Zambia Ministry of Health (RZMOH, 2016). Zambia has the lowest level of MC acceptability among the 10 Sub-Saharan African countries with high HIV incidence. To attain the Zambian national goal of 2 million VMMCs by 2020, innovative “demand generation” strategies will be required to increase the acceptability of VMMC, and thereby, to reach the desired increases in the rates of circumcision nationally (RZMOH), 2016).

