Exploratory analyses. To investigate change in EIMC attitudes, Stages of Change scores will be examined over time using an autoregressive modeling approach specifying the individual's stage at 1-week postpartum as the main outcome and individual's stage at baseline as a main predictor in the regression model (Hamaker et al., 2015). Variables from the previous path model will be included as potential covariates in attempting to explain stage movement. The estimated regression coefficient will reflect changes in EIMC attitudes over time. The model will use an ordinal logistic model to examine change over time. Odd ratios will be estimated as a measure of effect size (Chen et al., 2010).

Power. Using a two-tailed Z test to test the difference in proportions between two conditions at an α level of .05, this study has over 80% power to detect a difference of 6.0% in EIMC rate between the two conditions. This difference in proportion translates to an effect size of an odds ratio (OR) = 2.4, which is considered a small (OR = 1.68) to medium (OD = 3.47) effect size, according to Chen et al. (2010). This 2.4 OR is based on an effect size found in previous research examining circumcisions ([name] et al., 2015). With these specified parameters, 80% power is achieved with 140 couples (out of ~151 couples with male infants).

Data Security. CAB and FGD participants will not provide any uniquely identifying information during participation in group discussion sessions. Pregnant couple participants in the intervention will be assigned a unique code upon entering the study. This number will identify all participant files, which will include no identifiable information. Access to the computer data files will be restricted by password codes. The list translating participant number to identifying information

IRB Study Number:

Version #, Date:

will be maintained in a secure locked file in the Spear & Shield study office in Lusaka at the University of Zambia School of Medicine. Participants will be made explicitly aware at the time of the informed consent of the nature of the separate record that will be kept for them. CAB and focus group discussions will be audio-taped for review and summary of key discussion points; copies will be stored in a locked cabinet at the PI's Lusaka offices, and deleted following summarization.

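### Hypothesis 3 compares experimental with observation clinics, but its planned test sets the enrolled group against a fixed external rate of about 5% and leaves out the observation clinics' concurrent counts

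*Combined protocol and SAP*

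**What the plan says.** The Objectives section states Hypothesis 3 as "The S&S + LFLS experimental condition clinics will have higher numbers of EIMC in comparison with observation condition clinics". Section 14 repeats it in stronger form ("experimental condition clinics will have significantly higher numbers of EIMC in comparison with observation condition clinics") and lists, among the planned analyses, "a test of comparison between conditions". The Power paragraph says that "this study has over 80% power to detect a difference of 6.0% in EIMC rate between the two conditions", using 140 couples out of about 151 expected to have male infants.

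The H3 paragraph of section 14 specifies the test: "To compare the proportion of EIMCs in the experimental group to the proportion found in the observation group, a one-sample z-test will be conducted". It continues: "The population proportion will be taken to be the midpoint of the findings" of one published study and of historical circumcision numbers from Zambian clinics and hospitals. On that basis, "the percentage of EIMCs in the observation group is anticipated to be approximately 5.0" (percent).

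Section 12 (Design) randomises eight clinics, four per condition. The observation clinics enrol nobody and supply aggregate counts only. Item 8 of the assessments in section 12 collects 12 months of historical data and then monthly EIMC counts from month 6 to month 30. Section 24 says that clinics are matched before randomisation.

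The only provision for clustering, "A sandwich estimator will be used to account for the nested data structure", is in the H2 path-model text.

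**The concern.** A one-sample test compares one observed proportion with a constant. If the constant comes from outside the trial, the monthly counts from the four randomised observation clinics cannot influence the result. The test then asks whether enrolled couples differ from 5%. It does not ask whether experimental clinics did better than observation clinics, which is what Aim 3 and Hypothesis 3 are about.

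The error rates therefore hold only if the true background is close to 5%. If it is much lower, a real increase can be missed or even reported as significantly lower. If it is higher, an intervention with no effect can look successful. EIMC uptake is a primary endpoint (section 11), and section 12 links success in this pilot to planning a clinical trial.

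**Working it through.** **Inputs from the documents**
- Null 5%, difference 6 points (so 11%), two-sided alpha 0.05, n = 140 (section 14, H3 and Power).
- EIMC rates: about 0.3% nationally (Objectives); about 0.02% in EIMC-trained Lusaka clinics and 11% in the cited study of pregnant women (section 6).
- More than 150 births per clinic per month (section 9).

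**Assumptions, because the documents give no figure**
- Half of births are male.
- ICC 0.01, 0.02 or 0.05.
- 35 enrolled infants per experimental clinic (140/4).

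**1. The plan's own power figure**

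One-sample z: power = Φ([0.06·√140 − 1.96·√(0.05·0.95)] / √(0.11·0.89)) = Φ((0.7099 − 0.4272)/0.3129) = Φ(0.904) = **81.7%**. The figure reproduces against a known 5%.

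**2. The same figure when the comparator is estimated (pooled two-sample z, no clustering)**
- 140 vs 140: Φ((0.06 − 1.96·0.03243)/0.03223) = **46%**.
- 140 vs 5,400 observation-clinic male births (4·150·0.5·18 months): Φ((0.06 − 1.96·0.01892)/0.02661) = 80.5%.
- 140 vs 7,500 (4·150·0.5·25 months): 80.9%.

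So 80% holds for a known or very large comparator when clustering is ignored. Applying the design effect 1 + (m − 1)·ICC in both groups (m = 35 and 1,350 or 1,875):

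| ICC | Effective n, experimental vs observation | Power |
|---|---|---|
| 0.01 | 104 vs 373–380 | 59% |
| 0.02 | 83 vs 193–195 | 45% |
| 0.05 | 52 vs 79 | 26% |

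These are optimistic, because they use normal critical values with only four clinics per arm.

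**3. How the planned test behaves away from 5%**

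At n = 140 the expected count under the null is 7, with SD √(140·0.05·0.95) = 2.579. Rejection is outside 7 ± 1.96·2.579 = 1.95 to 12.05, so 13 or more reads as higher and 1 or fewer as lower. Binomial probabilities:

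| True rate in enrolled infants | Declared lower | Declared higher |
|---|---|---|
| 0.3% (for example, no effect at a 0.3% background) | 93% | about 0 |
| 1% (a rise from 0.3%) | 59% | about 0 |
| 5% (no effect at 5%, or a rise from 0.3%) | 0.6% | 2.4% |
| 8% (no effect at an 8% background) | about 0 | 33% |

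**4. Clustering in the planned test**

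With beta-binomial counts in four clinics of 35 and a true rate of 5%, 13 or more occurs with probability 4.4%, 6.4% and 10.6% at ICC 0.01, 0.02 and 0.05. The unclustered figure is 2.4%.

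**5. Support for the constant**

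The documents' own rates give midpoints of (11 + 0.3)/2 = 5.65% and (11 + 0.02)/2 = 5.51%. These are near 5%, but a midpoint of two values so far apart does not estimate the background rate in the trial's clinics.

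**The case against.** - **The 5% may be only a planning value.** The H3 paragraph opens by naming the observation group, and its last sentence uses the language of anticipation. But the sentence between them fixes the population proportion from other sources, and the test is named as one-sample. If a two-sample test was intended, the paragraph still needs correcting.
- **The historical source might include the study clinics' own past counts.** The text does not rule this out. They would then enter only as part of a fixed constant, and the concurrent counts would still be unused.
- **The power figure agrees with the one-sample test, and nobody proposed 140 vs 140.** Both points are right. The conflict is with how the Power paragraph describes the comparison. The 46% shows only that the claim depends on treating the comparator as known or nearly so. The 81.7% is also a normal approximation; with the cutoff of 13, exact power at 11% is 77.9%.
- **The low-rate scenarios may not apply to consenting couples who attend six sessions.** This is fair. Uptake among them could be near the 11% seen after information in the cited study. A verdict of lower at a true 0.3% is also correct as a statement about 5%. Setting the null above the background is conservative for declaring benefit, and false success needs a background above 5%, which no general clinic or national figure in the documents shows.
- **The ICCs have no source in the documents.** They show the direction of the error, not its size.
- **This is a feasibility pilot.** That excuses low power. It does not excuse reporting a comparison with a constant as a comparison with randomised controls.

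**Conclusion.** The concern holds. As written, the only test of Hypothesis 3 does not test it. The observation clinics' concurrent counts enter no stated hypothesis test, and no clustering allowance is given for H3. This follows from the text and needs no assumption.

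The size of the error depends on the unknown background rate. On the low clinic and national rates in the documents, the likelier harm is a missed or misdescribed increase: a true rise from 0.3% to 5% would be declared higher only 2.4% of the time. False success is the less likely direction. The 80% power is correct arithmetic for a known or nearly known comparator without clustering, but it does not describe a comparison of four clinics with four. Pilot status limits the consequences, and the observation counts could still expose a mismatch, although no stated rule uses them.

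**What to change.** Reconcile the Hypothesis 3, H3 and Power paragraphs of section 14.

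1. Replace the test against 5% with a comparison of the four experimental and four observation clinics. Use the concurrent monthly EIMC counts, take account of the 12 historical months, treat the clinic as the unit and follow the matching. Fix the analysis window in advance. Report an estimate with a 95% CI. One suitable form is each clinic's change in mean monthly EIMCs from its historical period, with a t interval (3 df if paired, 6 if not). Other clinic-level forms would also do.
2. Report the enrolled-couple proportion with a CI that allows for clustering. If male-birth denominators exist, comparing it with the observation-clinic proportion is supportive only, because it sets consenting couples against all births.
3. State that the 80% treats the comparator as known or nearly so, ignores clustering, and is not the power of the clinic-level comparison.

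The cost is SAP wording and one analysis of counts already collected. The downsides should be stated:

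- **Low power.** Simulation of the example analysis used Poisson noise only, no between-clinic variation and an effect in enrolled couples only, with their uptake at 11%. It declared higher about 15% (3 df) or 20% (6 df) of the time at a 0.3% background, and about 3.5% at 5%.
- **Dilution.** Over months 6–30 there are 150·0.5·25 = 1,875 male births per clinic, and 151/4 = 37.75 enrolled infants are 2.0% of them. A rise from 5% to 11% in those infants adds 37.75·0.06 = 2.3 EIMCs and moves the clinic rate to about 5.12%. At a 0.3% background, reaching 11% adds 37.75·0.107 = 4.0 to an expected 5.6.
- **Window.** Enrolment starts in month 7 in women up to 6 months pregnant, so the first births fall at about month 10. Over months 10–30 (1,575 male births per clinic) the figures become 2.4%, 5.14%, and 4.0 added to 4.7.
- **Precision for enrolled couples.** With 151 infants at 11%, the half-width is 1.96·√(0.11·0.89/151) = 5.0 points. Allowing for clustering, it is 5.8, 6.6 or 8.4 points at ICC 0.01, 0.02 or 0.05.
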